3. The subject has a screening hemoglobin (Hb) value as follows:
 - Any subject with a G6PD value $\geq 70\%$ of the site median value must have a screening Hb value ≥ 7 g/dL.
 - Female subjects with a G6PD value is $\geq 40\%$ - <70% of the site median value must have a screening Hb value ≥ 8 g/dL.

4. The subject has a QTcF of <450 msec.

N.B. Reading based on an average of triplicate ECGs obtained over a brief recording period by machine or manual over-read.

Efficacy

5. The subject has a positive malarial smear for *P. vivax*.
6. The subject has a parasite density of >100 and <100,000/ μ L.

Other

7. Male or female subject aged 16 years or older (18 years or older in Ethiopia) at the time of signing the informed consent.
8. The subject agrees to G6PD genotyping.
9. The subject is willing and able to comply with the study protocol.
10. The subject or parent/legal guardian, as applicable, has given written informed, dated consent; and the subject has given written assent, if applicable, to participate in the study.

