6.1. Critical Baseline Assessments

Written, dated informed consent must be obtained from each potentially eligible subject (or his/her legal representative) by study site personnel **prior** to the initiation of any screening procedures.

Clinical and laboratory assessments will be conducted at screening (**prior to first dose of the study medication**) as detailed in the Time and Events ([Table 2](#)).

- Demographic data will be collected to include details of date of birth, gender, race and ethnicity
- Medical history will be collected

- A physical examination will be conducted including:
 - Cardiovascular examination
 - Abdominal examination including assessment of splenomegaly
 - Respiratory examination

- Vital signs will be assessed. These include height, weight, temperature (oral, axillary or tympanic), heart rate, respiratory rate, systolic and diastolic blood pressure

- Investigators will assess *P. vivax* malaria symptoms at baseline. The incidence and severity (defined as absent, mild, moderate, severe, or unknown) of the following symptoms will be recorded: chills and rigours, headache, dizziness, abdominal pain, anorexia, nausea, vomiting, diarrhea, pruritis or itching, and coughing. The date of onset of symptoms will also be recorded. The investigator or designee can also assess and record any other *P. vivax* malaria symptoms.

- Blood smears for parasitological assessment will be collected and examined for asexual parasite count and gametocyte blood count (see Section [6.3](#) and the SPM for further details).

- A blood sample will be collected on a filter paper and stored for future plasmodium genotyping analysis. An additional blood sample will be collected to conduct exploratory plasmodium whole genome sequencing.

- Current and prior medications will be reviewed including any anti-malarial medication that has been used.

- G6PD status will be assessed using quantitative spectrophotometric analysis (further instructions can be found in the SPM). The quantitative analysis will

be used to determine the subject's eligibility for the study. One or more G6PD rapid point of care tests may also be performed at baseline.

- Periodic external quality assurance testing will be performed to ensure high quality G6PD assay data. Procedures for quality assurance will be described in detail in the SPM.
- A blood sample will be collected on Day 2 for G6PD and CYP2D6 genotyping.
- Laboratory Assessments:

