8.3.4.7. Exploratory G6PD & CYP-2D6 Genotype Analyses

All treated female and any male subjects meeting the pre-specified criteria for Hb deficiency (Hb decrease $\geq 30\%$ or ≥ 3.0 g/dL, or an overall drop below 6 g/dL) will be examined for mutations in the G6PD gene to investigate the relationship between G6PD

enzyme level, Hb and genotype. Genetic strategies most likely to be used include single nucleotide polymorphism (SNP) genotyping and/or direct DNA sequencing of subject DNA samples. The same genetic approaches may be used to investigate G6PD genotype in subjects that do not meet the pre-specified criteria for G6PD deficiency to allow relationships between G6PD enzyme level, Hb and genotype to be explored.

In addition, exploratory CYP-2D6 genotype analyses will be undertaken to test the hypothesis that null and/or intermediate metabolisers of 8-aminoquinoline drugs are more at risk of *P. vivax* relapse [Bennett, 2013].

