1.1. RAP Amendments

RAP Section	Amendment Details
Reporting and Analysis Plan_StudyTAF116564_Final [05-AUG-2016]	
Reporting and Analysis Plan_StudyTAF116564_Final_Amend 1 [21-FEB-2017]	
1.0, 4, 8.1.2, 10, 13.14.4, 13.14.8	Removal of Pharmacogenetics population – not required. mITT and Safety populations are sufficient as CYP2D6 and G6PD genotyping are collected under the main Informed Consent.
7.1.2	Correction of Newcombe upper confidence limit equation
8.1.2, 13.14.4, 13.14.5, 13.14.11	
Secondary Statistical Analyses: Re-design of efficacy analysis tables to display Cox Proportional Hazard and Kaplan-Meier results in one display
 
Sensitivity Analyses: By Genetic Classification: re-design of analyses to look at heterologous and homologous infections separately with new censoring rules
 
Sensitivity Analyses: Chloroquine Supply: Additional analyses included to

RAP Section	Amendment Details
	investigate the effect of chloroquine supplied before and after a cut-off date Secondary Statistical Analyses: Early Failures: Inclusion of category of early failures where the parasite genetics are missing; listing added Secondary Statistical Analyses: CYP2D6: minor changes to the output statistics
8.2.2, 13.14.6	Urine concentration change from baseline removed as no continuous urinalysis data is collected
13.6.3	Laboratory Parameters: Standard text on handling non-detectable lab values added
13.6.4	Relapse-free efficacy at 6 months and 4 months definitions: censoring added to account for subjects that take a concomitant medication with anti-malarial action prior to clearance plus clarification to the time periods assessed for 4 months Genetic classification of relapse definition: added to include censoring rules Recrudescence definition: clearance definition updated in line with other efficacy endpoints Fever clearance definition: updated to reflect Time and Events schedule of temperature collection
13.10.1	Addition of chloroquine supply covariate
Various	Typographical errors corrected

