8.2.2.1. Haemoglobin Declines and Related Laboratory Parameters

For all subjects with a drop in haemoglobin > 20 g/L, G6PD enzyme activity will be plotted against maximum drop in haemoglobin up to and including the Day 29 visit, with separate pages for each treatment group (Figure 3.35). Within the plot, different symbols will be used for the following categories:

- subjects who were genotyped and had a mutation classified as World Health Organization (WHO) class 1
- subjects who were genotyped and had a mutation classified as WHO class 2
- subjects who were genotyped and had a mutation classified as WHO class 3
- subjects who were genotyped and had a mutation of unknown significance
- subjects who were genotypically normal or had a mutation classified as a normal variant (WHO class 4)
- subjects who were not genotyped or did not have an evaluable genotyping result

A second plot will include only females with a drop in haemoglobin > 20 g/L (Figure 3.36), with separate pages for each treatment group, and a third for G6PD deficient males only (Figure 3.37).

A further set of plots will be produced for each treatment group for all subjects with non-missing G6PD genotype results, with males and females plotted on separate pages. Mean change from baseline haemoglobin will be plotted for G6PD normals by visit, up to and including Day 60 (Figure 3.38). Error bars will be plotted at each time point. Mean change from baseline haemoglobin for G6PD deficient males will also be plotted on the same

graph. It is anticipated that the number of G6PD deficient subjects will be very low, so all change from baseline values will be plotted for all G6PD-deficient subjects, but no error bars will be produced.

A further plot by treatment group will display mean change from baseline haemoglobin for all male subjects where G6PD genotype is unknown (Figure 3.39). This plot will cover all visits up to and including Day 29. Error bars will be plotted at each time point.

If a subject has a >20g/L decline from baseline haemoglobin or is a female who was genotyped and found to be G6PD deficient, a haematological profile plot will be produced for the subject (Figure 3.41). This will display their haemoglobin, absolute reticulocyte, methaemoglobin and bilirubin results (total and indirect bilirubin on same plot) at each visit. The subject ID, treatment group, sex, age and G6PD status should be included as a header for each subject's plot.

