3.23.	Safety	LB9	Boxplot of Clinical Chemistry Parameters by Visit and Treatment Group – Creatine Kinase		SAC

Safety : Figures					
No.	Population	IDSL / TST ID / Example Shell	Title	Programming Notes	Deliverable
3.24.	Safety	LB9	Boxplot of Clinical Chemistry Parameters by Visit and Treatment Group – Urea		SAC
3.25.	Safety	LB9	Boxplot of Clinical Chemistry Parameters by Visit and Treatment Group – Creatinine		SAC
3.26.	Safety	LB9	Boxplot of Clinical Chemistry Parameters by Visit and Treatment Group – Alkaline Phosphatase		SAC
3.27.	Safety	LB9	Boxplot of Clinical Chemistry Parameters by Visit and Treatment Group – Alanine Amino Transferase		SAC
3.28.	Safety	LB9	Boxplot of Clinical Chemistry Parameters by Visit and Treatment Group – Aspartate Amino Transferase		SAC
3.29.	Safety	LB9	Boxplot of Clinical Chemistry Parameters by Visit and Treatment Group - G6PD enzyme activity		SAC
3.30.	Safety	LB9	Boxplot of Change from Baseline in Clinical Chemistry Parameters by Visit and Treatment Group - G6PD enzyme activity		SAC
3.31.	Safety	LB9	Boxplot of Total Bilirubin by Visit and Treatment Group – Males		SAC
3.32.	Safety	LB9	Boxplot of Total Bilirubin by Visit and Treatment Group – Females		SAC
3.33.	Safety	LB9	Boxplot of Indirect Bilirubin by Visit and Treatment Group – Males		SAC
3.34.	Safety	LB9	Boxplot of Indirect Bilirubin by Visit and Treatment Group – Females		SAC
3.35.	Safety	SF1	Maximum Fall in Haemoglobin over First 29 Days by Enzyme Activity and Treatment Group	Subjects with decline of >20g/L in haemoglobin only	SAC

Safety : Figures					
No.	Population	IDSL / TST ID / Example Shell	Title	Programming Notes	Deliverable
3.36.	Safety	SF1	Maximum Fall in Haemoglobin over First 29 Days by Enzyme Activity and Treatment Group - Females	Subjects with decline of >20g/L in haemoglobin only	SAC
3.37.	Safety	SF1	Maximum Fall in Haemoglobin over First 29 Days by Enzyme Activity and Treatment Group – G6PD Deficient Males	Subjects with decline of >20g/L in haemoglobin only	SAC
3.38.	Safety	SF2	Mean Change from Baseline in Haemoglobin by Treatment Group, Visit and G6PD status (Subjects with Known G6PD Genotype)		SAC
3.39.	Safety	SF2	Mean Change from Baseline in Haemoglobin by Treatment Group and Visit (Male Subjects with Unknown G6PD Genotype)		SAC
3.40.	Safety	LB11	LFT Profile Plots	Only for subjects with >3 ULN in ALT or AST. Add footnote to this effect. The subject ID, treatment group, sex, age and race should be included as a header for each subject's plot.	SAC

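### Unless every male is assayed, the male page of RAP Figure 3.38 over-represents men with large haemoglobin falls, because such a fall is what commits a male to G6PD genotyping

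*Supplement*

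**What the plan says.** **Who is genotyped.** Protocol Amendment 5, section 8.3.4.7, commits to examining the G6PD gene in "All treated female and any male subjects meeting the pre-specified criteria for Hb deficiency". The criteria are a fall of at least 30% or at least 3.0 g/dL, or a value below 6 g/dL. For everyone else the wording is permissive: "The same genetic approaches may be used to investigate G6PD genotype in subjects that do not meet the pre-specified criteria for G6PD deficiency". No selection rule or target number is given.

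**Who could be genotyped.** Protocol 6.1 states: "A blood sample will be collected on Day 2 for G6PD and CYP2D6 genotyping". Inclusion criterion 8 in 4.2.1 reads "The subject agrees to G6PD genotyping". RAP 1.1 adds that "CYP2D6 and G6PD genotyping are collected under the main Informed Consent". So a sample and consent should exist for every male, but none of these sections says that every male's sample is assayed.

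**What is plotted.** In RAP 8.2.2.1 (amendment 1), Figure 3.38 covers "all subjects with non-missing G6PD genotype results, with males and females plotted on separate pages", and "Mean change from baseline haemoglobin will be plotted for G6PD normals by visit, up to and including Day 60", with error bars. Values for G6PD-deficient males go on the same graph without error bars. Figure 3.39, listed in 13.14.7 as "Mean Change from Baseline in Haemoglobin by Treatment Group and Visit (Male Subjects with Unknown G6PD Genotype)", runs to Day 29. Neither section says which males were assayed or carries a caveat.

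**The concern.** For males, a large haemoglobin fall triggers genotyping, and genotyping decides which figure a man appears in. Both figures plot haemoglobin change, so membership of each male curve depends on the outcome shown. The curve labelled G6PD normal could make haemolysis in genotypically normal men look worse than it is, and could blur the contrast with deficient males on the same graph. Haemolysis by arm is the trial's main question, so a figure with this label will be read. The two figures stop at different days (60 and 29), so a reader cannot simply recombine them beyond Day 29.

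**Working it through.** No figure in the plan is in dispute, so none needs reproducing. The check has two parts.

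**1. Does the text produce the selection?**
- Males with a qualifying fall are assayed by rule. Other males are assayed with some unknown probability q.
- If q = 1, genotyped males are all males and the selection disappears. Figure 3.39 would then hold only failed or missing samples.
- If q is below 1, genotyped males over-represent large falls. Untyped males then include no qualifying fall, apart from failed or missing samples.
- RAP 8.2.2.1 provides a symbol for subjects who were not genotyped, and Figure 3.39 exists for males only. The RAP therefore expects some untyped subjects and expects them to be male. This also supports reading 8.3.4.7 as genotyping all treated females and applying the haemoglobin criteria to males only.

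**2. How large could it be?** The following is illustrative.

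Inputs (protocol 3.3.1, Phase II, TQ 300 mg): about 30% of subjects fell between 1.5 and 2.5 g/dL and 4% fell by more than 2.5 g/dL. So about 34% exceeded 1.5 g/dL.

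Assume that maximum fall is normal with mean m and SD s:
- s = (2.5 − 1.5) / (z(0.96) − z(0.66)) = 0.75 g/dL
- m = 1.5 − z(0.66) × s = 1.19 g/dL

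With the 3.0 g/dL cut and t = (3.0 − m)/s:
- share above the cut: P = 1 − Φ(t)
- mean above: H = m + s·φ(t)/P
- mean below: L = m − s·φ(t)/(1 − P)
- mean in genotyped males: [P·H + (1 − P)·q·L] / [P + (1 − P)·q]

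The SD was also raised to 1.0 and 1.25 with m held fixed, as a stress test; those values no longer match the Phase II percentages.

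| | SD 0.75 | SD 1.0 | SD 1.25 |
|---|---|---|---|
| Males above the cut | 0.8% | 3.5% | 7.4% |
| All males, mean maximum fall (g/dL) | 1.19 | 1.19 | 1.19 |
| Genotyped, q = 0 | 3.25 | 3.40 | 3.56 |
| Genotyped, q = 0.10 | 1.33 | 1.72 | 2.14 |
| Genotyped, q = 0.50 | 1.21 | 1.27 | 1.36 |
| Genotyped, q = 1 | 1.19 | 1.19 | 1.19 |
| Untyped, any q below 1 | 1.18 | 1.11 | 1.00 |

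At the committed minimum, the genotyped-male mean is roughly three times the all-male mean (3.25/1.19 = 2.7; 3.56/1.19 = 3.0). It rests on about 1, 4 or 7 men per 100. With half of the other males assayed, the excess is 0.02 to 0.16 g/dL. Figure 3.39 is too low by 0.02 to 0.19 g/dL.

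Protocol 8.2.1 assumes that nobody outside the deficient-female subgroup meets the primary endpoint. On that assumption, the male page would be empty at q = 0.

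**The case against.** A reader might infer that the male normals in Figure 3.38 are mostly men chosen for a large fall, that the distortion is about threefold, and that both male curves are seriously biased. The documents do not support that reading.

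- They do not say how many males are assayed. Universal sampling and consent, the permission to assay others, the planned error bars for normals, and the accountability table for G6PD genetic data in all randomised subjects (Table 5.1) all fit broad genotyping. The threefold figure needs optional genotyping near zero.
- It also compares means of each man's maximum fall. The figures plot means by visit, which would be smaller because nadirs come at different visits.
- The effect on Figure 3.39 is small in every scenario.

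Other points for the plan also stand. The titles disclose the known and unknown subsets. The figures are descriptive and not Headline deliverables. No hypothesis is tested, and the primary proportions and intervals do not use genotype. Unselected male haemoglobin data are already planned in Tables 3.26, 3.29 and 3.31 and Figure 3.14.

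One tempting remedy fails too. Defining normal males by enzyme activity alone would absorb any genotypically deficient man who passed the 70% screen, and the figure exists partly to show such men.

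None of this removes the gap. Sampling and consent are not assay, and a title that names a subset does not tell the reader that the outcome determined entry to it.

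**Conclusion.** The point holds for the male page of Figure 3.38. Unless all males are assayed, that curve over-represents men with large falls. The bias is severe if few other males are assayed and small if about half or more are. Figure 3.39 is only slightly affected. Female displays are unaffected if all treated females are genotyped, as 8.3.4.7 is best read. The primary haemolysis analysis and the by-sex tables are also unaffected.

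The direction follows from the text alone. The sizes rest on an assumed normal distribution, on the 3.0 g/dL criterion being the one that binds, and on maximum fall rather than visit means, so they show rough scale only. This is a modest fault in a descriptive display, worth correcting because the correction costs so little.

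**What to change.** In RAP 8.2.2.1 and the display list in 13.14.7:

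- For males, replace the known/unknown-genotype split with one mean-change curve per arm, over a common period. Include all males not found genotype-deficient (enzyme activity at least 70% of site median), whether or not they were genotyped.
- Overlay any genotype-deficient male as individual values without error bars, as the RAP already intends for deficient subjects.
- Drop Figure 3.39.
- Keep the genotype split for females.

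Alternatively, keep the male split only if every male's Day 2 sample is assayed, and say so in the RAP.

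The first option changes wording and one subset flag and removes one figure, with no new samples or assays. The second costs the additional assays on samples already scheduled. The downside of the first is that the male curve may contain a few deficient men who were never typed; a footnote should state this and give the number of males assayed in each arm.

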8.2.3. Overview of Planned Other Safety Analyses

Table 4 provides an overview of the planned analyses, with further details of data displays being presented in Appendix 14: List of Data Displays.

Table 4 Overview of Planned Other Safety Analyses

Endpoint / Parameter/ Display Type	Absolute			Change from BL		
	Summary		Individual	Summary		Individual
	T	F	L	T	F	L
ECG						
ECG findings	Y		Y			
ECG Values by Visit			Y	Y	Y ¹	
QTcF values by Category ² and Visit	Y			Y		
Maximum Change from Baseline QTcF Up to 72 hours Post Randomised Treatment				Y		
Vital Signs						
Vital Signs by Time Point and Treatment Group	Y		Y	Y		
Mean Arterial Blood Pressure by Timepoint and Treatment Group		Y				

Endpoint / Parameter/ Display Type	Absolute			Change from BL		
	Summary		Individual	Summary		Individual
	T	F	L	T	F	L
Ophthalmic Assessments³						
Retinal Abnormalities	Y		Y	Y		
Keratopathy	Y		Y			
Slit Lamp Assessments	Y		Y	Y		
Humphrey Perimetry Assessments	Y		Y	Y		
Colour Perception Assesments	Y		Y			
Best Corrected Visual Acuity Test Scores	Y		Y			
Best Corrected Visual Acuity Classification	Y		Y	Y		
Blood Transfusions						
Blood Transfusion	Y					

NOTES:

- T = Table, F = Figures, L = Listings, Y = Yes display generated
- Summary = Represents TFL related to any summaries (i.e. descriptive statistics) of the observed raw data.
- Individual = Represents FL related to any displays of individual subject observed raw data.
- ¹QTcF only
- ²QTcF categories defined in Section 8.2.3.1; include maximum post baseline rows
- ³Presentation of ophthalmic assessments described in Section 8.2.3.2
- Where triplicate assessments are performed (i.e. at baseline), the mean of the 3 assessments will first be derived and the summary statistics will be presented using the mean of the assessments.
- Temperature readings will be used in these summaries, regardless of the methodology of temperature assessment.

8.2.3.1. Electrocardiogram

QTcF categories for each post baseline timepoint (Table 3.39) are defined as:

- Absolute QTcF:
 - ≤ 450 msec
 - >450 to ≤ 480 msec
 - >480 to ≤ 500 msec
 - >500 msec
- Increase from baseline QTcF:
 - <60 msec
 - ≥ 60 and absolute QTcF ≤ 480 msec
 - ≥ 60 and absolute QTcF >480 msec

8.2.3.2. Ophthalmic assessments

Ophthalmic assessments will all be summarised for the Ophthalmic Safety population.

Each type of eye assessment (keratopathy (Table 3.43), slit lamp (Table 3.44), Humphrey perimetry (Table 3.45), colour perception (Table 3.46), and best corrected visual acuity (Table 3.47, Table 3.48)) will be summarised separately by eye, visit and treatment group, including maximum changes from baseline to any visit.

Keratopathy will be summarised by presenting the number of subjects with keratopathy at baseline, and at each visit. For each visit, the proportion of subjects displaying keratopathy and grade of keratopathy in the each eye will be summarised. The number and percentage of subjects with a new keratopathy at any post-baseline visit will also be presented in the same table (Table 3.43).

For best corrected visual acuity, summary statistics for the logMAR score will be displayed for each visit (Table 3.47). A separate tabulation (Table 3.48) will classify changes in logMAR score from baseline as no change (<0.12), possible change (≥ 0.12 to <0.3), or definite change (≥ 0.3) (see Section 13.6.3) for each visit and the maximum change from baseline.

For the colour perception data, the number of Ishihara plates missed will be summarised by visit, and maximum change from baseline, for each eye (Table 3.46).

For retinal data, hyperpigmentation (Table 3.49), hypopigmentation (Table 3.50), appearance of retinal vessel (Table 3.51), optic nerve pallor (Table 3.52), confounding abnormalities (Table 3.53) and retinal changes from baseline (Table 3.54) will be summarised. The number and percentage of subjects with each response (definite, absent, questionable, cannot read, not applicable) will be summarised by visit, eye and treatment group. For retinal changes from baseline, the categories will be no change, questionable change, definite change and cannot grade. The number and percentage of subjects with a definite result at any post-baseline visit, where it was absent or questionable at baseline, will also be included in each table.

9. PHARMACOKINETIC ANALYSES

PK and Population PK analyses will be the responsibility of Clinical Pharmacology Modelling and Simulation within GSK and will be detailed in a separate document.

